2.3. Scientific Rationale

The study will test two prebiotics: highly pure GOS and LacNAc-enriched GOS (hGOS). The intervention will include a dose of 15 g daily as previously reported¹⁰. Dose was selected based on previous literature reports^{16, 17, 28-30} and the interventions conducted by our group to assess efficacy of GOS in lactose-intolerant individuals^{10, 11, 31, 32}. The hGOS targeted dose will be composed of 15g of GOS enriched with 150 mg of LacNac (99:1), which is in agreement with the range found in human breast milk³³. Based on the concentration detected in breast milk, an infant consumes between 54 and 243 mg of LacNAc per day, with the variation depending on stage of lactation and infant age and weight.

Participants will be assigned randomly to one of 3 groups (n = 16): GOS, hGOS or placebo (powdered corn syrup comprised of fructose, glucose, and an inert cellulose material that matched the consistency, color, sweetness, and taste of the prebiotics)^{10, 32} to test safety and dose tolerability. The prebiotic treatment will last for 4 weeks, since we have shown in adult individuals that a 4-week period allows for the observation of changes to the gut microbiome^{10, 11}. The doses of GOS, hGOS and placebo will be increased over 28 days beginning with 10 g/day and increasing to 15 g/day. Dose regimen will be 5 grams twice daily on days 1–10 followed by 7.5 grams twice daily on days 11–28. Doses will be in powder form and will be mixed with water or food and taken as directed by the dosing scheme.

High-sensitivity C-reactive protein (hs-CRP) is a recognized marker of systemic inflammation³⁴ and specific pro-inflammatory cytokines mediate interaction between immune cells and non-immune cells, contributing to the inflammatory status of the intestine^{35, 36}. Based on previous studies with probiotics and prebiotics that report potential immunomodulatory effects³⁷⁻³⁹, we decided to monitor hs-CRP, IL-1 α , IL-1 β , IL-2, IL-6, IL-8, IL-12, TNF α , and IFNy for the duration of the clinical trial.

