Before the treatment (baseline) and during week 4 of the trial (after the prebiotic treatment), we will assess changes in quality and quantity in bacterial components of the gut microbiome pre- and post-treatment. Likewise, we will determine serum inflammatory markers, and integrity of the intestinal barrier at baseline and at week 4. Subjects will also respond to the Diet History Questionnaire (DHQ), a freely available food frequency questionnaire (FFQ) and will be asked to keep daily diet records.

3. Objectives

3.1. Specific Aim 1

To validate 15 g/day dose safety and tolerability of GOS and hGOS in **healthy adults**.

3.2. Specific Aim 2

To establish a biological signature of GOS and hGOS through assessment of prebiotics effects vs placebo on (i) abundance of beneficial gut bacteria and restoration of the gut microbiome saccharolytic potential, (ii) modulation of biomarkers of inflammation and (iii) evaluation of intestinal barrier function.

4. Study Design

[figure not shown]
This will be a controlled (GOS, hGOS versus placebo), interventional, longitudinal (baseline compared to end of study), prospective, single-site pilot study. Subjects will be assigned randomly to one of 3 groups (n = 16): GOS, hGOS or placebo. The treatment will consist in 10 - 15 g/day of GOS, hGOS or placebo (powdered corn syrup comprised of fructose, glucose, and an inert cellulose material that matched the consistency, color, sweetness, and taste of the prebiotics), which will be provided to participants as powder that can be added to any non-alcoholic beverage or sprinkled on food for intake. The intervention will last for 4 weeks, since we have shown in adult individuals that a 4 week period allows for the observation of changes to the gut microbiome. The study will end after the second time-point sample collection at 4 weeks.

Dose rationale: The intervention will include a dose of 5 grams twice daily on days 1–10 followed by 7.5 grams twice daily on days 11–28¹⁰. Doses were selected based on previous literature reports^{16, 17, 28-30} and the interventions conducted by our group to assess efficacy of GOS in lactose-intolerant individuals^{10, 11, 31, 32}. The hGOS preparation will be composed of GOS enriched with LacNac at a concentration of 6.7–31µg/mL (<1% of the formulation), which is in the range found in human breast milk³³ and hence considered safe.

Flow diagram

Prior to Enrollment

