- (2) Determination of levels of biomarkers of inflammation (IL-1 α , IL-1 β , IL-2, IL-6, IL-8, IL-12, TNF α , and IFNy) as well as high-sensitivity C-reactive protein, a marker of low-grade inflammation (hsCRP) in serum. We will determine cytokine levels using the MCYTOMAG-70K (Milliplex) in the Advanced Analytics Core (AAC) of the CGIBD. (ii) hsCRP concentration will be measured via hsCRP ELISA (Sigma Aldrich).

Measurements in stool:

Determination of abundance of beneficial bacteria (*Bifidobacterium* and *Akkermansia* species) in the gut microbiome of treatment and placebo groups and the microbiome saccharolytic potential using WGS sequencing, the most accessible, cost-effective measure currently available.

4.4.Outcome Measures

Primary Outcome(s):

The expected outcome is to confirm a 15 g/day as a safe and tolerable dose of GOS and hGOS in healthy adult individuals using the 38-point Gastrointestinal Symptom and Severity Checklist (GSSC).

Secondary Outcome(s):

Definition of prebiotic biosignature characterized by:

- Increased abundance of saccharolytic bacteria (*Bifidobacterium*) and other beneficial bacteria (*Akkermansia*)
- Modulation of biomarkers of inflammation
- Improved intestinal barrier function.

Tertiary/Exploratory Outcome(s): N/A

Other Measures: Baseline Characteristics and Assigned Treatments: N/A

5. Study Participants

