7.8. Premature Discontinuation

If a subject withdraws or the investigator discontinues subject participation after Visit 1, data from that visit will be included in the analysis of Objective 1, but not Objective 2

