9.2. Aim-Specific Plans

Plans for Aim 1 (A1): Validate 15 g/day dose safety and tolerability (absence of GI adverse effects) of GOS and hGOS in healthy adults.

Method. We will report descriptive statistics for demographics, basic medical history, prescription and over the counter, and dietary supplements, including means and standard deviations for continuous variables, and percentages and ranges for categorical data. We will report the number and percent of all individuals (intent to treat) who had any adverse event (prompted or in response to an open-ended question). We will also report the number and percent of events over time, as well as the severity of the event.

Statistical analysis for A1. Data will be presented as mean \pm SD for variables that are normally distributed, or median (IQR) for variables not normally distributed. Binary/categorical outcomes will be reported as a percentage with confidence interval.

Plans for Aim 2: Establish a biological signature of GOS and hGOS through assessment of prebiotics effects vs placebo on:

(A2.1) Abundance of beneficial gut bacteria and restoration of the gut microbiome saccharolytic potential

Method. Determination of abundance of beneficial bacteria (*Bifidobacterium* and *Akkermansia* species) in the gut microbiome of treatment and placebo groups and the microbiome saccharolytic potential by Whole Genome Shotgun (WGS) sequencing⁵⁵. For assignment of saccharolytic (SAC) and non-saccharolytic (NON_SAC) phenotypes we will use the reference study by Vieira-Silva *et al.*²⁶ as described⁹.

Statistical analysis (A2.1). we will perform both exploratory analysis and statistical testing for changes in plasma cytokines. Data will be presented as mean \pm SD. To find the change of microbiome abundance under difference circumstance, Mann-Whitney-Wilcoxon matched pair tests between baseline and 4 weeks follow-up will be performed for abundance of beneficial gut bacteria in each treatment arm. To compare the change of microbiome abundance in three arms, we will apply the Kruskal-Wallis test whether the change of microbiome abundance is the same among three groups. Due to multiple testing was proposed in A2.1, p values will be corrected for the total number of comparisons with a controlled false-discovery rate (FDR)

ditching statistical significance: Looking beyond a much used and abused measure would make science harder, but better. *Nature* 567, 283-283.

(A2.2) Modulation of biomarkers of inflammation

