- (3) Temporal relationship – Is there a reasonable temporal relationship between the time of onset of the event and the administration of the investigational product?
- (4) Concomitant medication – Is the event a known side effect of a concomitant medication?

Based on the previous factors we will consider the following descriptions when assessing relationship of an event to the investigational product:

Definite: There is a reasonable causal relationship between the investigational product and the AE, when the event responds to withdrawal of the investigational product (de-challenge) and recurs with re-challenge by administration of the investigational product.

Probable: There is a reasonable causal relationship between the investigational product and the AE. The event responds to de-challenge. Re-challenge not required.

Possible: There is a reasonable causal relationship between the investigational product and the AE. De-challenge is lacking or unclear.

Not Likely: There is a temporal relationship between the investigational product administration and the AE, but there is not a reasonable causal relationship between investigational product and the event.

Unrelated: There is not a temporal or causal relationship to the investigational product administration.

The Investigator will record causal relationship in the source documents, as appropriate, and report such an assessment in accordance with the SAE reporting requirements, if applicable.

Expectedness Definition: An assessment of expectedness will be performed for each AE and SAE. Previously reported expected effects of prebiotic administration include abdominal pain (cramps), bloating, flatulence (gas) and diarrhea (loose stools >3 times/day). During the study, GI side effects will be expected and only AEs that are meet the definition of severe AE or considered an SAE will be reported to the IRB or FDA.

AE and SAE Assessment, Follow-up Procedures: The Investigator will record all directly observed AEs and all AEs spontaneously reported by the study subject beginning from the time the subject begins use of the investigational product through 7 days after the last dose of the investigational product. Changes in health status after the subject has provided informed consent but before the subject begins use of the investigational product shall be recorded as changes in the medical history.

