The Investigator will assess subjects at each visit for the occurrence of AEs. In order to avoid bias in eliciting AEs, subjects should be asked the following non-leading question: "Have there been any changes in your health since your last visit?"

All AEs (serious and non-serious) reported by the subject must be recorded regardless of if a causal relationship with the investigational product is suspected. Each AE will be assessed to determine if it meets the criteria for a serious adverse event (SAE). If an SAE occurs, expedited reporting will follow local and international regulations as appropriate.

Reporting and Documentation Procedures: AE and SAE reporting periods will extend from the signature of the informed consent through the End of the Study Visit or until 7 days after the last dose of the investigational product. If an SAE occurs, [name] will be notified within 24 hours of awareness of the event by the Investigator. This timeframe also applies to adding new information (follow-up) on previously forwarded SAE reports. In the rare event that the Investigator does not become aware of the occurrence of an SAE immediately, the Investigator will report the event within 24 hours of first awareness of the SAE and document the time of his/her first awareness of the SAE. For all SAEs, the Investigator will pursue and provide information to the Sponsor or designee in accordance with the timeframes for reporting specified above. This will generally include a description of the AE in sufficient detail to allow for a complete medical assessment of the case and independent determination of possible causality. Information on other possible causes of the event, such as concomitant medications and illnesses must be provided. All observed or volunteered AEs regardless of treatment group or suspected causal relationship to the investigational product(s) will be reported.

Participant Notification of New Information:

Participant will be notified via email, text message and/or phone call.

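### The dose after a symptom-triggered step-down is 10 g/day in one section and 7.5 g/day in two others, and the Aim 1 summary never counts who stayed on 15 g/day

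*Combined protocol and SAP*

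**What the plan says.** Section 3.1 states the aim: "To validate 15 g/day dose safety and tolerability of GOS and hGOS in" healthy adults. Section 4.4 words the primary outcome the same way: "The expected outcome is to confirm a 15 g/day as a safe and tolerable dose". The regimen in 2.3 is titrated, "beginning with 10 g/day and increasing to 15 g/day", with 5 g twice daily on days 1–10 and 7.5 g twice daily on days 11–28.

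For Aim 1, section 9.2 reports the "number and percent of all individuals (intent to treat) who had any adverse event", the "number and percent of events over time", and severity, with binary outcomes given as a percentage with confidence interval. Sections 4.3 and 8.1 add drop-out, adherence and weekly symptom scores as tolerability measures.

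The rules for a two-level increase over baseline on the listed PROMIS items are:

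| Section | Early rule | Later rule | Reduced dose |
|---|---|---|---|
| 6.7 | withdraw in the first 10 days | reduce once day 10 has passed | 5 g twice daily, reassess in 3 days |
| 10.2 | withdraw in the first 10 days | reduce once 10 days are exceeded | one sachet of 7.5 (printed mg) per day |
| 10.4 | discontinue in the first 10 days | reduce from 10 days onward | one 7.5 g sachet per day |

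Under 6.7, a participant who tolerates the lower dose carries on in the trial at that dose. Section 10.1 describes intake as 7.5–15 g/day; the synopsis and sections 4 and 4.1 say 10–15 g/day.

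**The concern.** Two problems sit together here.

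The first is operational. Staff dealing with a symptomatic participant have two instructions for the same trigger, and one of them cannot be carried out with the pouches dispensed. On day 10 itself, 10.4 supports both stopping and reducing.

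The second is a gap in the analysis. The question is whether people can take 15 g/day. Someone withdrawn in the first 10 days never takes that dose, and someone who steps down at day 14 spends most of the second phase below it. Both belong in an intent-to-treat percentage for the regimen. That percentage does not show how many people could remain on 15 g/day, or at which daily dose the symptoms began. A stepped-down participant is not a drop-out, and may be fully adherent to the reduced dose, so the other planned tolerability measures do not reveal them either.

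**Working it through.** **Planned exposure (2.3).** 10/28 = 36% of days at 10 g/day; 18/28 = 64% at 15 g/day.

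**Kit (6.1, 6.3, 7.4).** 10 × 2 = 20 pouches of 5 g and 18 × 2 = 36 of 7.5 g. The total is 56, which reproduces the label. One spare of each size makes the 58 stated in 6.1. Packets for all 28 days are handed out at Visit 1, and no re-supply is described.

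**Supply needed after a step-down.** If the reduction starts the day after a contact on day d, there are 28 − d reduced days. The 6.7 dose then needs 2 × (28 − d) sachets of 5 g, and the 10.2/10.4 dose needs 28 − d sachets of 7.5 g. Scheduled 7.5 g pouches still unused are 36 − 2 × (d − 10).

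| Contact | Reduced days | 5 g needed (6.7) | 5 g left | 7.5 g needed (10.2/10.4) | 7.5 g left, before spare |
|---|---|---|---|---|---|
| Day 14 (12–16) | 14 (16–12) | 28 (32–24) | 1 spare | 14 (16–12) | 28 (32–24) |
| Day 21 (19–23) | 7 (9–5) | 14 (18–10) | 1 spare | 7 (9–5) | 14 (18–10) |

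Even the 3-day reassessment in 6.7 needs 3 × 2 = 6 sachets of 5 g. Pouches set aside after missed doses (4.1) could add a few. One 7.5 g sachet per day is always covered.

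**Dose received by a stepped-down participant, days 11–28.**
- Step-down at day 14: 14/18 = 78% of second-phase days are below 15 g/day. The mean is (4 × 15 + 14 × 10)/18 = 11.1 g/day under 6.7, or (4 × 15 + 14 × 7.5)/18 = 9.2 g/day under 10.2/10.4.
- Step-down at day 21: 7/18 = 39% of days. The mean is (11 × 15 + 7 × 10)/18 = 13.1, or (11 × 15 + 7 × 7.5)/18 = 12.1 g/day.

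**How far the over-time summary helps.** Contact 1 (days 5–9) lies in the 10 g/day phase. Contact 3 (days 19–23) and the final visit (days 26–30) come well after the switch. Contact 2 (days 12–16) is the main one that straddles it. The open question in 10.3 asks "Have there been any changes in your health since your last visit". If that means since contact 1, it looks back over 10 − 9 = 1 to 10 − 5 = 5 days at 10 g/day, nominally 3 of 7. If it means since Visit 1, it covers all 10 such days, nominally 10 of 14. So time gives an approximate split by scheduled phase, but it does not follow the dose actually taken after a reduction.

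**Denominator and precision of an added percentage.** The documents disagree on numbers. Section 8.6 randomises 45 (45/3 = 15 per arm). The synopsis enrols 48 (48/3 = 16). Sections 8.6 and 9.4 enrol 55–60, and 9.5 recruits 60 and reaches 16 per arm only after 20% drop-out (60/3 = 20 before it). With assumed counts and exact (Clopper-Pearson) 95% intervals:
- 16/20 = 80% (56% to 94%)
- 12/15 = 80% (52% to 96%)

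**The case against.** The strongest reply is that the regimen is titrated by design, so an any-event percentage over the whole regimen is a proper summary, and early withdrawals rightly count in it. This stands. A reader might infer that the intent-to-treat percentage is wrong, or that early withdrawals contaminate it. The documents do not support that, and the measure proposed here also keeps everyone randomised.

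It can also be said that tolerability is covered elsewhere, through drop-out, adherence by pouches left (6.6), weekly PROMIS scores and recorded reasons for withdrawal. Much of this stands, and most contacts fall within one scheduled dose phase. What remains is an explicit count of step-downs. The medical monitor's look at dose (6.7, 10.2) follows only the 5-of-20 trigger and is not an Aim 1 analysis.

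Three other stronger readings should be set aside:
- Section 7.8 says "data from that visit will be included in the analysis of Objective 1, but not Objective 2". A reader might take this to keep all post-dose data of withdrawn participants in Objective 1. The visit named is Visit 1, the baseline; it is the intent-to-treat wording in 9.2 that keeps these people in.
- A reader might blame the conflicting step-down doses for mixing doses after day 10. A single reduced dose would still leave people on 15 g/day and on less in the same period.
- The mg in 10.2 might look like a third dose. It is evidently a unit slip; the 6.1 label has the same slip for the spare packets.

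Finally, 10.1 supports 7.5 g as the reduced dose, so 6.7 may simply be the outlying text. That makes the correction easier but does not remove the conflict.

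**Conclusion.** The reduced-dose conflict is an error in the protocol as written: 10 g/day (10/15 = 67% of target) against 7.5 g/day (7.5/15 = 50%) for the same event. The 10 g/day version lacks supply by a wide margin. The overlap at day 10 in 10.4 is a smaller error of the same kind. Both bear on how a symptomatic participant is handled and should be corrected.

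The Aim 1 part is a cheap improvement, minor to moderate in a descriptive pilot. The planned percentage describes the regimen. It needs a companion that describes 15 g/day, because no planned summary identifies people who step down and stay in the trial.

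The supply figures assume that reduction starts the day after a contact and that nothing is re-supplied. The number of step-downs is not given in the documents and is not estimated here. The percentages with intervals use assumed counts and show precision only.

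**What to change.** **Correct the protocol.**
- State one reduced dose in 6.7, 10.2 and 10.4, and align the stated dose range in 10.1, the synopsis and sections 4 and 4.1. One 7.5 g sachet per day needs no new supply; if 10 g/day is preferred, provide extra 5 g sachets.
- Change mg to g in 10.2 and on the label in 6.1.
- Use one boundary throughout, such as withdrawal through day 10 and reduction from day 11. Say whether symptom onset or the questionnaire date decides. Section 10.2 can be read as turning on when the symptom occurred, so this has to be written down.

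**Add to Aim 1 in 9.2, keeping the intent-to-treat percentage.**
- By arm, the number and percent with confidence interval of all randomised who reached and stayed on 15 g/day to day 28. Count early withdrawals and step-downs as not staying on it, and show reasons, since some (such as antibiotic use, 6.4) have nothing to do with tolerability. Settle the number randomised first.
- A descriptive table by arm of adverse events and two-level PROMIS increases by daily dose at onset. Record onset day and daily dose at onset on the weekly form if they are not already there; 10.3 already weighs the "time of onset of the event and the administration of the investigational product" in judging relatedness, and the form itself is not among the documents.

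**Cost.** Wording changes in a few sections, up to two form fields, one table and one percentage, with no extra contacts. The drawbacks are small cells and onset dates that rely on recall.

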Statistical Analysis Plans	Data will be presented as mean \pm SEM for variables that are normally distributed, or median (IQR) for variables not normally distributed. Group means will be compared by ANOVA and post hoc tests except when data is normally distributed (a nonparametric analysis of medians will be performed using the Kruskal-Wallis test for non-normally distributed data). Chi-square tests or Fisher's exact tests will be used for incidence data. For analysis of microbiome taxonomic and functional data we will carry out Mann-Whitney-Wilcoxon matched pair tests for pairwise comparisons between time points. Unpaired Mann-Whitney-Wilcoxon tests will be used for pairwise comparisons between treatment groups. We will apply the Kruskal-Wallis test when more than two groups are compared. P values will be corrected for the total number of comparisons with false-discovery rate (FDR).

2. Introduction: Background and Scientific Rationale

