Rationale. High-sensitivity C-reactive protein (hs-CRP) is a recognized marker of systemic inflammation³⁴ and specific pro-inflammatory cytokines mediate interaction between immune cells and non-immune cells, contributing to the inflammatory status of the intestine^{35, 36}. Based on previous studies with probiotics and prebiotics that report potential immunomodulatory effects³⁷⁻³⁹, we decided to monitor hs-CRP, IL-1 α , IL-1 β , IL-2, IL-6, IL-8, IL-12, TNF α , and IFN γ for the duration of the clinical trial.

Method. Determination of levels of biomarkers of inflammation (IL-1 α , IL-1 β , IL-2, IL-6, IL-8, IL-12, TNF α , and IFN γ) as well as high-sensitivity C-reactive protein, a marker of low-grade inflammation (hsCRP) in serum. We will determine cytokine levels using the MCYTOMAG-70K (Milliplex) in the Advanced Analytics Core (AAC) of the CGIBD. hsCRP concentration will be measured via hsCRP ELISA (Sigma Aldrich).

Statistical analysis (A2.2). Similar to A2.1, we will perform an exploratory analysis of changes in plasma cytokines. Data will be presented as mean \pm SD. To find the change of biomarker of interest under difference circumstance, paired t-test for matched pair between baseline and 4 weeks follow-up will be performed for levels of biomarkers in each treatment arm. To compare the change of biomarker level in three arms, we will use ANOVA to test whether the change of biomarker level is the same among three groups. Due to multiple testing, p values will be corrected for the total number of comparisons with a controlled false-discovery rate (FDR)

(A2.3) Evaluation of intestinal barrier function.

Method. Blood samples will be drawn and serum will be used to quantify zonulin using the Zonulin (IDK® Zonulin) (Serum) ELISA test (Immundiagnostik AG). Zonulin is a biomarker of impaired intestinal permeability, which has been associated with various disorders^{56, 57}.

Statistical analysis (A2.3). Since A2.3 has similar data and analytic goal as A2.2, the analytic approach will be the same as what we proposed in A2.2.

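### Aim 2 is about effects versus placebo, but section 9.2 names no GOS-placebo or hGOS-placebo difference, uses change scores without a baseline covariate, and drops the synopsis's between-arm pairwise and post hoc tests

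*Combined protocol and SAP*

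**What the plan says.** Section 3.2 sets Aim 2: "To establish a biological signature of GOS and hGOS through assessment of prebiotics effects vs placebo on" beneficial bacteria and saccharolytic potential, inflammation markers and barrier function. Section 9.2 then plans two kinds of test for each part.

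- **A2.1 (microbiome).** Within arms, "Mann-Whitney-Wilcoxon matched pair tests between baseline and 4 weeks follow-up will be performed for abundance of beneficial gut bacteria in each treatment arm". Across arms, "we will apply the Kruskal-Wallis test whether the change of microbiome abundance is the same among three groups".
- **A2.2 (eight cytokines and hsCRP).** Within arms, "paired t-test for matched pair between baseline and 4 weeks follow-up will be performed for levels of biomarkers in each treatment arm". Across arms, "we will use ANOVA to test whether the change of biomarker level is the same among three groups".
- **A2.3 (zonulin).** Here "the analytic approach will be the same as what we proposed in A2.2".

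A2.1 and A2.2 both apply an FDR correction across all the comparisons made, and A2.3 inherits this.

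Three other places bear on the point. The statistical row of the synopsis says, for microbiome data, "Unpaired Mann-Whitney-Wilcoxon tests will be used for pairwise comparisons between treatment groups", and it mentions unspecified post hoc tests after ANOVA. Section 9.a item (5) promises a CI or an SE with every estimate. Section 9.5 says that means and standard errors of the inflammation markers will be compared.

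**The concern.** The question is comparative, and two comparisons answer it: GOS with placebo and hGOS with placebo. Section 9.2 specifies neither. A within-arm test asks whether an arm changed over four weeks, which can happen for reasons unrelated to the product. The omnibus test asks whether the three arms differ somewhere, which includes GOS differing from hGOS. As 9.2 is written, the report could consist of within-arm p-values, one omnibus p-value per outcome and arm means with SDs, with no stated effect of either product against placebo.

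The synopsis and 9.2 also disagree on whether between-arm follow-up tests will be done. Section 9.a says that the plan is fixed before data collection, and section 6.2 says that the team is unblinded before analysis. A contrast not named in advance would therefore be chosen by people who know the allocation.

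**Working it through.** **1. The plan's own figure.** Section 9.5: 60 recruited, 20% dropout, so 60 × 0.8 = 48 and 48 / 3 = 16 per arm. This reproduces. Other figures appear elsewhere: 48 enrolled (synopsis, 5.1), 45 randomised (8.6) and n=20 (9.5, inflammation markers). If 48 are enrolled and 20% leave, 48 × 0.8 / 3 = 12.8, about 13 per arm. The documents give no effect size, SD, correlation or alpha for Aim 2. Below, two-sided alpha 0.05 and normal data are assumed.

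**2. What 9.2 supplies.** Per outcome there are 3 within-arm tests and 1 omnibus test, with no placebo contrast. A2.2 has 9 markers, so 27 + 9 = 36 tests. A2.3 has 3 + 1 = 4. A2.1 cannot be totalled because the number of species tested is not stated. If all three between-arm pairwise tests are added, the count per outcome is 3 + 1 + 3 = 7.

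**3. What the omnibus test can show.** Noncentrality is n × Σ(mᵢ − m̄)², with 2 and 45 df and means in SDs of change.

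| True pattern, n = 16 | Noncentrality | Power |
|---|---|---|
| One active arm differs from the other two arms by 1 SD | 16 × 2/3 = 10.67 | 81.4% |
| Both active arms differ from placebo by 1 SD | 16 × 2/3 = 10.67 | 81.4% |
| hGOS, placebo, GOS in 0.5 SD steps | 16 × 0.5 = 8 | 68.6% |

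The first two patterns mean different things for the products, yet the test cannot separate them. In the third, neither product is more than 0.5 SD from placebo.

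**4. What the within-arm tests can show.** Suppose all arms shift equally by 0.5 SD of change, so there is no effect versus placebo. Each paired t-test at n = 16 has power p = 0.465. The chance that at least one active arm is significant while placebo is not is (1 − p) × [1 − (1 − p)²] = 0.535 × (1 − 0.286) = 0.38. With no shift, p = 0.05 and the chance is 0.95 × (1 − 0.9025) = 0.09. Both are per outcome and before FDR. The shift is an assumption.

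**5. The shared FDR family.** Assume Benjamini-Hochberg at 5%; neither the procedure nor the level is stated. In the 36-test A2.2 family, a lone ANOVA result needs p ≤ 0.05/36 = 0.0014 if no other test is significant, and p ≤ 28 × 0.05/36 = 0.039 if all 27 within-arm tests are. These are the two ends of the range, not an expectation. Nine ANOVAs corrected alone would need 0.05/9 = 0.0056. So the corrected between-arm p-value depends on tests that say nothing about placebo.

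**6. Baseline as a covariate, serum markers only.** Let r be the correlation between baseline and week 4, with equal SDs at both times. The variance ratio, adjusted to change score, is (1 − r²) / [2(1 − r)] = (1 + r)/2. The 95% half-widths in SDs of the marker are

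- change score: t(3n − 3) × √[2(1 − r) × 2/n]
- adjusted: t(3n − 4) × √[(1 − r²) × (2/n) × (1 + 1/(3n − 4))]

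| Assumed r | Variance ratio | n = 16: change v adjusted | n = 13 | n = 20 |
|---|---|---|---|---|
| 0.3 | 0.65 | 0.84 v 0.69 | 0.94 v 0.77 | 0.75 v 0.61 |
| 0.5 | 0.75 | 0.71 v 0.62 | 0.80 v 0.70 | 0.63 v 0.55 |
| 0.7 | 0.85 | 0.55 v 0.51 | 0.62 v 0.58 | 0.49 v 0.46 |
| 0.9 | 0.95 | 0.32 v 0.31 | 0.36 v 0.35 | 0.28 v 0.28 |

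The n = 20 column reads the figure in 9.5 as a number per arm; 9.5 does not say what it counts. None of this applies to the rank tests in A2.1.

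**The case against.** The strongest reply is that this is a drafting inconsistency rather than a missing analysis. Section 9.2 does compare the arms, and on change, so baseline is already subtracted. The synopsis belongs to the same document and plans pairwise tests. Section 9.a promises a CI or SE. If the means and SDs reported for the serum markers are those of the changes, a reader can work out each unadjusted difference and its CI by hand. Section 4 describes the study as longitudinal, so within-arm comparisons are part of the declared design. Aim 2 is secondary, and 9.5 admits low power for the inflammation markers.

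Much of this stands, and it limits the point. It does not remove it. An SE on each arm mean would satisfy 9.a without any placebo contrast being reported, a rank-test p-value is not an estimate, and the synopsis and 9.2 still differ.

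A reader might infer more than the documents support:

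- *That ignoring baseline biases the comparison.* It does not. Change scores are unbiased under randomisation, and only a covariate is missing.
- *That all of the synopsis's pairwise tests were dropped.* The matched-pair tests between time points are kept in 9.2. Only the between-arm pairwise and post hoc tests are missing.
- *That the shared FDR family inflates false positives.* With no effect and no shift, a simulation of nine independent markers (16 per arm, 20,000 runs at each r) gave about a 2% chance of any false ANOVA result in the shared family, against about 5% for the nine ANOVAs alone. The shared family is looser only under a large shift common to all arms, which no section predicts.
- *That Aim 2 itself demands a CI, or that 9.5 says no effect size exists for any Aim 2 outcome.* Section 3.2 mentions no CI. The missing effect size in 9.5 concerns the inflammation markers only; its microbiome paragraph cites consistent earlier increases.

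**Conclusion.** The point holds as a mismatch between the aim and its analysis. Section 9.2 leaves the two placebo comparisons undefined, and the tests it does list cannot show which product differs from placebo. That follows from the text and needs no assumption.

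The gain from a baseline covariate is real but depends on r, which the documents do not give. At 16 per arm the half-width shrinks by 0.15 SD at r = 0.3 (0.84 − 0.69) but only 0.01 SD at r = 0.9 (0.32 − 0.31). This assumes normal data and equal SDs. No power gain is claimed. Taking the within-arm tests out of the FDR family is justified because the placebo result should not depend on them, not because error is inflated.

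The consequence is confined to how the secondary and exploratory biosignature is read. The primary tolerability result is unaffected.

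**What to change.** In 9.2, and in matching words in the synopsis:

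1. Name the GOS-placebo and hGOS-placebo differences as the main Aim 2 estimates, each with a 95% CI.
2. For the serum markers (A2.2 and A2.3), estimate these differences at week 4 with the baseline value as a covariate.
3. For A2.1, keep rank methods and give each placebo contrast on change as a rank-based difference with a CI, for example a Hodges-Lehmann shift.
4. Apply the FDR correction to the placebo contrasts: 2 × 9 = 18 in A2.2, 2 in A2.3, and 2 per outcome tested in A2.1.
5. Keep the within-arm comparisons, labelled as supportive because they do not test an effect versus placebo. The omnibus tests can remain as sensitivity analyses.

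Transformations, detection-limit rules and the handling of zeros are optional details and not part of this point.

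The cost is a change of wording and slightly more analysis work. Baseline and week-4 samples are already scheduled. The downside is that the covariate adds little precision when r is high.
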